9.5.1.3.3 CEREBROSPINAL FLUID SAMPLING

Amyloid CSF is 1 of the 2 methods available for screening to determine subject eligibility for the study. (revised per Amendment 03) Subjects who undergo the eligibility CSF sample collection or who consent to the CSF longitudinal substudy will be encouraged to stay at the site after completion of LP for medical observation. CSF sample(s) will be collected by LP (gravity drip method only) after fasting (preferred), or at least 2 hours after the most recent meal.

CSF samples at Visit 13 should be collected while the subject is still on the study drug and before the other visit assessments. All ED CSF samples need to be taken no later than 7 days

after the last dose of study drug. All CSF samples should be taken at approximately the same time of day as at the Screening Visit. (revised per Amendment 06)

Subjects who provide a CSF sample at Screening for amyloid eligibility purposes, but did not initially consent to the CSF longitudinal substudy may provide consent to the CSF longitudinal substudy at any point in time up to the CSF procedure at Visit 13 (or ED). INR results should be reviewed for subjects who consent to provide a CSF sample and are on concomitant anticoagulation/antiplatelet therapy, before LP; if they are assessed by the investigator to be at risk for bleeding, they are to be excluded from CSF collection. (revised per Amendments 01 and 02)

9.5.1.4 Pharmacokinetic, Pharmacodynamic, Pharmacogenomic, and Other Biomarker Assessments

9.5.1.4.1 PHARMACOKINETIC ASSESSMENTS

Blood samples will be collected for the determination of the concentrations of elenbecestat in all randomized subjects. Analyses of metabolite concentrations may be performed, depending on emerging data from other studies with elenbecestat. Samples from all subjects receiving active treatment will be analyzed. Placebo samples will be held in storage in the event that confirmatory analysis is requested. (revised per Amendment 04) Plasma concentrations of analytes will be quantified by liquid chromatography with tandem mass spectrometry methodology using a previously validated assay.

Blood samples will be collected as specified in [Table 4](#) and [Table 5](#). Two plasma PK samples will be obtained at each of the following visits: 1 sample at predose (trough) and another sample 1 to 6 hours postdose at Visits 3, 4, 6, 7, 9, and 11 and another sample 4 to 8 hours postdose at Visit 13 (or ED). Therefore, subjects or their study partners must be instructed not to take their study drug at home on the day the PK sampling is performed. Instead, subjects will take the study drug at the clinic after collection of the predose PK sample. At Visit 13 (or ED), the trough PK blood sample should be collected shortly before or after completing the LP for subjects participating in the CSF substudy. If the study drug is temporarily suspended, postdose PK samples will not be required. If at an ED Visit, the subject has already stopped study drug, postdose PK samples are not required. (revised per Amendment 06)

Blood will also be drawn where possible at the first report of an SAE or severe unexpected AE and at its resolution.

See the laboratory manual (to be supplied to study sites) for a description of the collection, handling, and shipping procedures for PK samples.

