- v: Site staff will contact the subject or the study partner the day before the PK blood sampling to provide instructions that subjects must not take their study drug at home on the day of the PK blood sampling. During this telephone contact with the subject or the study partner, the site staff should document the time that the subject took their study drug that day, ie, the day before the PK blood sampling.
- w: Two plasma PK samples will be obtained: 1 sample at predose (trough) and another sample 1 to 6 hours postdose at Visits 3, 4, 6, 7, 9, and 11 and another sample 4 to 8 hours postdose at Visit 13 (or ED). Therefore, subjects or their study partners must be instructed not to take their study drug at home on the day the PK sampling is performed. Instead, subjects will take the study drug at the clinic after collection of the predose PK sample. At Visit 13 (or ED), the PK blood sample should be collected shortly before or after completing the LP for subjects participating in the CSF substudy. If the study drug is temporarily suspended, postdose PK samples will not be required. If at an ED Visit, the subject has already stopped study drug, then postdose PK samples are not required.
- x: PD and exploratory biomarker blood samples should be collected at fasting or at least 2 hours after the most recent meal and, as far as is feasible, samples should be taken at the same time of day at all visits. Samples should be taken predose at Visits 2, 3, 4, 6, 7, 9, 11, 13 (or ED), 14, and 15. (revised per Amendments 01, 03, and 04)

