- y: For subjects who consent to participate in the CSF longitudinal substudy. Visit 13 (or ED) also includes blood PK and PD assessments and so the subject will be dosed at the clinic on these days. A CSF sample will be collected by LP between 4 and 8 hours postdose and at the same time of day as the subject's Screening LP (±1 hour). The CSF sample will be taken with the subject fasting (preferred) or at least 2 hours after the most recent meal. A gravity drip collection method must be used. If performed on the same day as the cognitive tests, the LP will be performed after the cognitive tests; the subject should rest and drink some fluid to hydrate after the cognitive tests and before the LP. Subjects will be encouraged to stay at the site after completion of LP for medical observation. The CSF sample will not be taken at the ED Visit if this visit occurs within 39 weeks of treatment or 3 months of a previous CSF sample. If at an ED Visit, the subject has already stopped study drug, then no dosing will take place, but the CSF sample will still be collected unless it was already collected within the past 3 months. Subjects receiving concomitant anticoagulation/antiplatelet therapy should have prothrombin time and INR (derived from prothrombin time) before LP; if they are assessed by the investigator to be at risk for bleeding, they are to be excluded from CSF collection. Note that subjects who are assessed by both amyloid PET and CSF are required to wait for a minimum of 48 hours between the 2 procedures. (revised per Amendments 01, 02, and 04)
- z: Subjects reporting AEs relating to abnormal dreams, nightmares, or sleep terror will be questioned on the nature, frequency, and impact of these events.
- aa: AEs that may signal drug abuse potential require a more detailed follow-up through completion of a specific eCRF form (Possible drug abuse potential form/questionnaire). Similarly, AEs

Table 5 Schedule of Procedures/Assessments in Study E2609-G000-301 (Revised per Amendments 05 and 06)

Phase Period	Randomization													Follow-Up			UNS Visit ^d
	Treatment												ED ^b	14 ^c	15 ^c		
Visit ^a	2	3	4	5	6	7	8	9	10	11	12	13					
Day	1	15	29	57	85	183	274	365	456	547	638	729		757	813		
Week	1	3	5	9	13	27	40	53	66	79	92	105		109	117		
Weeks elapsed since 1st dose	0	2	4	8	12	26	39	52	65	78	91	104		108	116		
Nominal months elapsed since 1st dose	0		1	2	3	6	9	12	15	18	21	24		25	27		
Procedures/ Assessments																	

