9.7.1.7.2 PHARMACOKINETIC-PHARMACODYNAMIC

The PK/PD relationship between CSF biomarker levels and plasma PK parameters or CSF concentrations of elenbecestat will be explored graphically and any emergent relationship will be explored through population PK/PD modeling. These PK parameters include maximum observed concentration (C_{max}), and $AUC_{(0-24)}$ derived from the population PK model. The PK/PD relationship between plasma PK parameters and CSF concentrations of elenbecestat with other biomarkers may also be explored using similar methods.

Additionally, the relationship between various PK parameters (eg, C_{max}) or CSF concentrations of elenbecestat and CDR-SB at 24 months, and the relationship between various PK exposure parameters or CSF concentrations of elenbecestat and the change from Baseline for 24 months in ADAS-cog14, and the MMSE, will be explored graphically. Any emergent relationships will be explored through population PK/PD modeling. The relationship between exposure to elenbecestat and most frequent AEs will also be explored.

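### On a Visit 13 (or ED) day with a clinic dose, the PK and CSF timing rules cannot all be met, so the single on-treatment CSF sample has no consistent time relative to dose

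*Protocol*

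**What the plan says.** Section 9.5.1.4.1 plans two plasma PK samples at each PK visit. One is a predose sample, which the section equates with trough. The other follows the dose, at 1 to 6 hours at Visits 3, 4, 6, 7, 9 and 11, and at 4 to 8 hours at Visit 13 (or ED). Subjects do not dose at home on these days; "subjects will take the study drug at the clinic after collection of the predose PK sample". For CSF-substudy subjects at Visit 13 (or ED) the section adds that "the trough PK blood sample should be collected shortly before or after completing the LP for subjects participating in the CSF substudy".

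Table 5 note w repeats the sampling plan, but its pairing sentence reads only that "the PK blood sample should be collected shortly before or after completing the LP"; the word trough is absent.

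Table 5 note y says the subject is dosed at the clinic on the Visit 13 (or ED) day. It continues: "A CSF sample will be collected by LP between 4 and 8 hours postdose". It also puts the LP after the cognitive tests when both fall on the same day. If the subject has already stopped drug at an ED Visit, no dose is given.

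The synopsis (Study Design) and Sections 9.1.2 and 9.1.2.1 say that CSF and PET assessments come before any other visit assessments, with the subject still on drug. Section 9.5.1.3.3 says the same of the Visit 13 CSF sample.

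**The concern.** Three rules meet on one day: the trough comes before the dose, the trough goes with the LP, and the LP follows the dose by 4 to 8 hours. A fourth rule, CSF before everything else, sits uneasily with the third. A site coordinator must break at least one of them, and nothing in the protocol says which.

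The stake is the quality of one measurement. Section 9.2.4 limits the CSF substudy to a single time point at 24 months, so a mistimed Core Study sample cannot be recovered. That sample supplies several things:
- the CSF amyloid-beta and tau biomarker endpoints (Section 9.7.1.1.3), tested between arms at two-sided 0.05 (Section 9.7.1.7.3);
- the CSF drug concentration, used as an exposure variable in Section 9.7.1.7.3;
- the work in Section 9.7.1.7.2 on "The PK/PD relationship between CSF biomarker levels and plasma PK parameters or CSF concentrations of elenbecestat".

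If time since dose differs between sites for reasons of wording, CSF drug concentration, and possibly CSF amyloid-beta in the active arm, carry variability that the design did not intend.

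**Working it through.** This is a check of sampling windows; the plan states no figure to reproduce. Let t be hours from the clinic dose on a dosing day.

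**Inputs**
- Predose (trough) sample: t ≤ 0 (Section 9.5.1.4.1, dose given after it).
- LP: 4 ≤ t ≤ 8 (Table 5, note y).
- Second Visit 13 plasma sample: 4 ≤ t ≤ 8 (Section 9.5.1.4.1; note w).
- Once-daily dosing, so the next trough is at about t = 24.

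**Trough against LP**
- Trough before that day's dose: the gap is at least 4 − 0 = 4 h, and at least 8 − 0 = 8 h if the LP is at the end of its window.
- Trough before the next day's dose: the gap is 24 − 8 = 16 h to 24 − 4 = 20 h.
- Neither is shortly before or after the LP, so the windows do not overlap.

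**Postdose sample against LP**
- The windows are identical. The gap can be 0 h, and is at most 8 − 4 = 4 h if the two are not tied.

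**CSF before other assessments against note y**
- If the LP comes first on the Visit 13 day, it precedes the PK sampling and hence the dose, at about 24 h after the previous day's dose. That breaks the 4 to 8 hour rule and places CSF 16 to 20 h later in the dosing interval.
- It also breaks note y's order of cognitive tests first, then LP, on the same day.
- An LP on a separate earlier day could satisfy the ordering rules, but the trough-against-LP conflict above would remain.

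**What a site can do on a dosing day**

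| Site's choice | CSF time since dose | Plasma beside CSF? | Rule broken or datum lost |
|---|---|---|---|
| LP at 4 to 8 h, so-called trough drawn with it | 4 to 8 h | Yes | Predose sample lost or mislabelled |
| LP beside a true trough, then dose | about 24 h | Yes | Note y's LP window |
| True trough, LP at 4 to 8 h, postdose plasma in the same window | 4 to 8 h | Available | Pairing sentence in 9.5.1.4.1 |

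No row satisfies every rule. Across rows, CSF falls at two quite different points in the dosing interval.

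The protocol gives no half-life for elenbecestat and no size for the CSF substudy, so neither the concentration error nor the number of subjects affected can be computed.

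**The case against.** The best case for the plan has five parts.

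1. **Mispairing.** A reader might infer that plasma and CSF will be mispaired by 4 to 8 hours in the PK/PD analysis. The documents do not support that. When a site ties a plasma sample to the LP, the two are simultaneous. When it does not, a separate 4 to 8 hour plasma sample is already scheduled. This objection stands; what remains is inconsistent CSF timing and a lost or mislabelled predose sample.

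2. **Wrong sample.** A reader might also infer that Section 9.5.1.4.1 simply names the wrong sample and needs one word changed. The matching 4 to 8 hour windows make that tempting, but it is unproven. If CSF really precedes the other assessments, an LP beside the trough followed by the dose is feasible, and the out-of-step text would be note y. Changing one word would also leave the ordering rules in conflict with note y.

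3. **Model-derived exposure.** Section 9.7.1.7.2 takes plasma Cmax and AUC from the population PK model, informed by two samples at each of seven visits. True, and it protects the plasma side. It does not standardize when CSF was drawn, and CSF concentration is itself used directly.

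4. **Table 5 governs.** Section 9.5.1.4.1 sends sites to Table 5 for collection times, and notes w and y can be read together. That lowers the practical risk, but note w does not say which of the two samples it means, and the body text still says trough. The laboratory manual is not shown; it may help sites, but cannot remove a contradiction in the protocol.

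5. **ED Visits.** Where drug has already stopped, no dose is given and there is no conflict. This stands.

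**Conclusion.** On any Visit 13 or ED day with a clinic dose, the protocol's timing rules for the trough sample and the LP contradict each other, by at least 4 hours. A second inconsistency, CSF before other assessments against an LP 4 to 8 hours postdose and after same-day cognitive tests, leaves open whether CSF belongs early or late in the dosing interval, a difference of about 16 to 20 hours.

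The consequence is a foreseeable risk of added variability in CSF drug concentration, CSF amyloid-beta change and the exploratory CSF PK/PD analysis, and of lost or mislabelled predose samples. Its size depends on how sites actually behave and on the drug's kinetics, neither of which the document gives. It is confined to the optional CSF substudy and, for the predose sample, to those subjects' Visit 13 (or ED) plasma data. Primary and key secondary analyses are not affected.

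The conclusion rests on reading trough as predose, as Section 9.5.1.4.1 does, and on once-daily dosing. It does not say which schedule is right.

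**What to change.** Reconcile the synopsis (Study Design), Sections 9.1.2, 9.1.2.1, 9.5.1.3.3 and 9.5.1.4.1, and Table 5 notes w and y, so that they:
- give one LP time relative to the clinic dose, and one order relative to the other visit assessments;
- name the plasma PK sample that accompanies the LP, consistently with that time and in the same words everywhere;
- keep the predose sample before dosing;
- leave the exception for ED Visits where drug has already stopped.

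In the PK/PD data set, use actual dose, plasma and CSF clock times rather than nominal labels. For samples already taken, this shows which schedule each site followed.

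The cost is a wording change in a few places and a clarification to sites. No extra sample or visit is needed.

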9.5.1.4.2 PHARMACODYNAMIC, PHARMACOGENOMIC, AND OTHER BIOMARKER, ASSESSMENTS

[Table 2](#) lists PD, pharmacogenomic, and exploratory biomarker assessments. Key elements of these assessments are described below. (revised per Amendment 04)

Table 2 Planned Pharmacodynamic, Pharmacogenomic, and Other Biomarker Assessments (revised per Amendment 06)

Sample	Screening		Baseline		Treatment/Follow-up			
Whole Blood/ Plasma	PGx	Putative AD Diagnostic	PD	Example of Exploratory Biomarkers	PD	Example of Exploratory Biomarkers		
	ApoE ^a NAT2 ^b TREM2 ^b CD33 ^b EPHA1 ^b	microRNA tau:Aβ(1-42) Aβ42/Aβ40 ratio Aβ oligomers	Aβ(1-x)	NFL VILIP1 YKL-40 Tau	Aβ(1-x)	NFL VILIP1 YKL-40 Tau		
Sample	Eligibility		Baseline (CSF Substudy)		Treatment/Follow-up (CSF Substudy)			
CSF	CSF AD Biomarkers		PD	CSF AD Biomarkers	Example of Exploratory Biomarkers	PD	CSF AD Biomarkers	Example of Exploratory Biomarkers
	Aβ(1-42) Tau:Aβ(1-42) ratio		Aβ(1-x)	Aβ(1-42) tau p-tau (Subset) Aβ isoforms Aβ(1-40) Aβ(1-38)	NFL VILIP1 YKL-40 BDNF BACE1 Neurogranin	Aβ(1-x)	Aβ(1-42) tau p-tau (Subset) Aβ isoforms Aβ(1-40) Aβ(1-38)	NFL VILIP1 YKL-40 BDNF BACE1 Neurogranin

Aβ = amyloid beta, Aβ(1-x) = amyloid beta (1-x) (ie, the amyloid beta monomer from amino acid 1 to x [eg, 1-42]), AD = Alzheimer’s disease, *ApoE* = apolipoprotein E, BACE1 = beta-amyloid converting enzyme 1, BDNF = brain-derived neurotrophic factor, CD33 = sialic acid binding immunoglobulin-like lectin 3 (Siglec-3), CSF = cerebrospinal fluid, EPHA1 = erythropoietin-producing hepatoma receptor A1, NAT2 = N-acetyltransferase 2, NFL = neurofilament light, PD = pharmacodynamic, PGx = pharmacogenomics, RNA = ribonucleic acid, TREM2 = triggering receptor expressed on myeloid cells 2, VILIP1 = visinin like protein 1, YKL-40 = human cartilage glycoprotein-39 (HC gp-39)

a: mandatory for all subjects

b: to be analyzed in a subset of subjects

Biomarkers

The CSF sample will be used for PD and exploratory assessments including but not limited to CSF Aβ(1-x), Aβ(1-42), t-tau, and p-tau. (revised per Amendments 03 and 04)

The plasma samples will be used for Aβ(1-x) analysis and may be used for exploratory biomarker analyses. Aβ(1-x) in both CSF and plasma will be measured using a modified commercially available enzyme-linked immunosorbent assay (ELISA). The prescreening and postscreening analysis of CSF Aβ(1-42), t-tau, and p-tau will be performed using commercially available ELISAs. (revised per Amendments 03 and 04)

Blood samples will be collected for PD/exploratory biomarker assessments as specified in Table 4 and Table 5. (revised per Amendment 03) The blood sample collected for PD/exploratory biomarker analyses at Visit 2 should be collected at fasting or at least 2 hours after the most recent meal and PD blood samples should be taken predose at Visits 2, 3, 4, 6, 7, 9, 11, and 13 (or ED) and, as far as is feasible, samples should be taken at the same time of day. (revised per Amendment 04)

Prerandomization blood samples for immunologic assessments and CSF (if applicable) will also be stored for determination of prior exposure to any suspected infective agents in the

event that the subject develops TEAEs that warrant further investigation (eg, treatment-emergent infection). (revised per Amendments 03 and 04) Testing may include, but not be limited to, serological tests (eg, HSV1 and 2), viral titer by quantitative polymerase chain reaction (Q-PCR), and/or human leukocyte antigen (HLA) genotyping.

For all subjects, baseline and on-study blood samples, DNA samples, and any collected CSF samples (if applicable) will be stored for up to 15 years.

See the laboratory manual (to be supplied to study sites) for a description of the collection, handling, and shipping procedures of the biomarker samples.

Pharmacogenomics

A blood sample will be obtained at Screening and will be used to determine the *ApoE* genotype of all subjects enrolled in this study. NAT2 genotype will be evaluated in a subset of subjects. Genotype will be determined from blood specimens using validated assays. (revised per Amendment 04) The findings will be used in the statistical analysis to determine the effects on treatment response and safety. (revised per Amendment 01)

The genomic DNA samples will be stored and may also be used to examine the role of genetic variability in subjects' absorption, distribution, metabolism, and excretion, the development of AEs, or underlying AD. Variations in elenbecestat exposure or the occurrence of AEs observed in the study population may be evaluated by correlation of single-nucleotide polymorphisms with PK, safety, or PD data.

Details of PGx testing may be provided and reported separately.

Amyloid PET

An amyloid PET scan may be performed at Screening to confirm deposition of amyloid in the brain. A historical amyloid positive PET scan may be used if conducted within 12 months before the planned date of randomization and provided that the scan and result are considered acceptable by the central PET reading group. As part of an optional substudy, longitudinal amyloid PET imaging will also be conducted after 12 and 24 months of treatment (or at ED, provided the subject has received at least 39 weeks of study drug and at least 6 months has elapsed since the prior amyloid PET scan was performed). (revised per Amendment 04) Longitudinal amyloid PET imaging will only be conducted on subjects that have consented to this optional substudy and who have had Screening amyloid PET scans performed for this study (ie, historical amyloid PET scans cannot be used for the longitudinal analyses).

For subjects participating in the amyloid PET substudy, amyloid PET imaging will be conducted on separate days from the scheduled visits and should be conducted before the clinic Visit 9 and no later than 7 days after the last dose for Visit 13/ED. (revised per Amendment 06)

Descriptions and detailed instructions for all amyloid PET imaging can be found in the PET imaging manual provided to the study PET imaging facilities.

Tau PET (revised per Amendment 05)

A third longitudinal biomarker substudy (tau PET) will be offered to study-eligible subjects from select geographical sites (based on proximity to the tau PET ligand manufacturing sites) in the US who have an amyloid positive study-specific PET scan and who consent to participate in the amyloid PET substudy. For subjects who consent to the tau PET longitudinal substudy, tau PET imaging will be conducted during Screening (after amyloid positive PET results have been reported and before randomization) and again at 24 months (or at the ED Visit, provided the subject has received at least 39 weeks of study drug). At the 24-month timepoint (or at the ED Visit), the amyloid and tau PET scans can be performed in either order, but must be at least 48 hours apart. If the subject has also consented to the longitudinal CSF substudy, the longitudinal substudy assessments can be performed in any order, with at least 48 hours between each procedure.

For subjects participating in the tau PET substudy, tau PET imaging will be conducted on separate days from the scheduled visits and should be conducted before clinic Visit 13/ED and no later than 7 days after the last dose of study drug. (revised per Amendment 06)

Descriptions and detailed instructions for all tau PET imaging can be found in the tau PET imaging manual provided to the study tau PET imaging facilities that will be in select geographical locations in the US, based on proximity to the tau PET ligand manufacturing sites. (revised per Amendment 05)

Further details regarding pharmacodynamics, pharmacogenomics, and other biomarker research is provided in [Appendix 4](#).

